Each reagent receives a defined score and the final summation allows estimating the probabilistic category of the cause-effect relationship between the administration of the product under investigation and the adverse reaction, adverse event or suspected adverse reaction.

Table 5. Algorithm of Karch and Lasagna modified by Naranjo.

In such a way that the degree of certainty to establish the IP or investigational medication (as appropriate) as the causal agent of the harmful phenomenon that happens to the participating patient, can be indicated directly by the principal investigator based on his clinical experience or through the voluntary application of the tool mentioned previously. However, it is important that

the researcher and the UFTLS take into account the following arguments in favor of the causal relationship:

- B. Strength of association that refers to the number of cases in relation to those exposed.
- C. The consistency of the data, ie the presence of a common characteristic or pattern.
- D. The exposure-effect pattern: which determines the relationship with the site of onset, time, dose and reversibility after suppression.
- E. The biological plausibility: that refers to the possible pharmacological or physiopathological mechanisms involved in the development or presentation of the adverse event.
- F. Experimental findings: for example, the appearance of abnormal metabolites or high levels of drug or the product of its biotransformation.
- G. Analogy: experience acquired with other related drugs, adverse reactions frequently produced by the same family of pharmacological agents.
- H. Nature and characteristics of the data: objectivity, accuracy and validity of the relevant documentation. [71]

9.2.2 Responsibilities of the sponsor.

The sponsor will be responsible, and will cover the expenses derived from the medical attention to adverse events related to the IP.

9.3 Unanticipated problems.

The unanticipated problems (NAP) consider those situations that pose risks for the participating subjects, in general, any incident, experience or result that meets all the following criteria:

- Unexpected in terms of its nature, severity or frequency in relation to: 1) documents related to the study such as the researcher's manual, study protocol and informed consent format; and 2) the characteristics of the population being studied.
- Related or possibly related to your participation in the study (possibly related means that there is a reasonable possibility that the incident, or results, was caused by the study's own procedures).
- Indicative that the research places the participants at a higher risk of harm (including physical, psychological, economic or social) than previously recognized.

9.3.1 Report of PNAs.

The PI will be responsible for reporting PNAs to the sponsor, to the CI, to the CEI. The report must contain the following information:

- Identification of the study: protocol title and number, name of the PI and, where appropriate, the center.
- Detailed description of the event, incident, experience or result.
- Explanation, justification of the reasons why the incident represents an NAP.
- Description of changes to the protocol or corrective actions taken or proposed in response to the NAP.

The PNAs that are EAS must be reported to the CEI and the sponsor within the first 24 hours that the PI has knowledge of this.

Any other NAP will be reported to the CEI and the sponsor within the first 5 business days, after the PI has knowledge of this.

9.4 Audit.

To guarantee compliance with the PCBs and with all applicable regulatory requirements, Sophia Laboratories, S.A. of C.V. could carry out quality assurance audits. Regulatory agencies could also conduct a regulatory inspection of this study.

9.4.1 Pre-study audit.

The study centers included in the study will be subject to a feasibility visit prior to the selection of the center, where it will be verified that they meet the minimum requirements indicated by the sponsor.

9.4.2 Audit / Inspection during the conduction of the study.

They may take place at any time before, during or after the conclusion of the study. If an audit or inspection is conducted, the investigator and the institution must agree to allow the auditor / inspector direct access to all relevant documents, and will allocate their time and that of their staff to the auditor / inspector to discuss the findings and any relevant problems. In case the audit has not been scheduled by the sponsor, the center must notify Sophia Laboratories, S.A. of C.V. immediately.

10 Ethical considerations.

10.1 Approval of the committees.

The present study will be conducted according to the standards of the Declaration of Helsinki, World Medical Association 2013. Nuremberg Code; Nuremberg Trial by the International Tribunal of Nuremberg, 1947. Belmont Report, National Commission for the Protection of Subjects of Biomedical Research and Conduct, 1979. Will be conducted in accordance with scientific and technical requirements for the registration of medicines for use of the International Conference on Harmonization (The International Council for Harmonization, ICH) Guide to Good Clinical Practices. International Ethical Guidelines for Biomedical Research in Human Beings of the Council for International Organizations of Medical Sciences (Council for International Organizations of Medical Sciences, CIOMS, 2002). International Ethical Guidelines for epidemiological studies of the Council for International Organizations of Medical Sciences (Council for International Organizations of Medical Sciences, CIOMS, 2008). The Research Ethics Committee and the Research Committee will evaluate the protocol before conducting the study and will issue their approval or possible modifications for its realization, these Committees should be notified of any significant changes to the protocol. In addition to the above, the current regulations issued by the Ministry of Health will also be complied with. General Health Law, NOM 012 Official Mexican Standard NOM-012-SSA3-2012, Which establishes the criteria for the execution of research projects for human health. The study is considered as an investigation with a risk greater than the minimum according to the Regulation of the General Health Law on Health Research, Title Two, Chapter I, Article 17, Category III, published in the Official Gazette on 6 January 1987.

Principal investigators or study coordinators or personnel authorized by the sponsor will be evaluated by the Research Ethics Committees, Research Committees, and when applying to the Biosafety Committee the essential documentation of the research project: research protocol, letter of informed consent, researcher's manual, subject's diary, as well as those requested, in addition, according to local, national or international requirements applicable by regulatory entities.

The study will not start in the research site if you do not have the confidentiality agreements and economic proposal of each of the principal investigators, duly signed and without having previously obtained the favorable opinion and / or the approval of the Committees of Ethics in Research, Research Committees, and when applicable by the Biosecurity Committee, corresponding.

The study will not begin without having met the relevant local, national or international regulatory requirements and without having the corresponding health authorization.

10.2 Amendments to the protocol.

The amendment procedure will be relevant when there is a need to make any change to a document that is part of the research project or protocol, derived from variations in the methodological structure, substitution of the principal investigator or when identifying risks in the research subjects. The documents subject to amendment will be: protocol, letter of informed consent, researcher's manual, documents for the patient, scales of measurement and schedule of activities.

Any amendment must be approved by the sponsor and / or the principal investigator, the amended document (s), once reviewed and approved by the Research Ethics Committee and the Investigation Committee or when applicable, by the Board of Directors. Biosafety, (entities that issued the initial favorable opinion for the conduct of the investigation) will be sent (s) for authorization by the relevant regulatory entity.

Amendments that substantially modify the protocol, confers an additional or different risk on the research subjects, must be approved by the aforementioned Committees. It is the investigator's responsibility to take action in situations that require immediate action to avoid unnecessary harm to study participants.

The principal investigator has the responsibility to inform the Research Ethics Committee of any amendment to the protocol that could eventually affect the rights, safety or welfare of the research participants. Likewise, he must know any situation or new knowledge that will show a greater risk for the participants, the termination or premature suspension of the study, the reasons and the results obtained up to that moment. You must also inform about the conclusion of the study, when completing the research protocol.

10.3 Early termination of the study.

The study may be temporarily suspended or terminated prematurely if there is a sufficiently reasonable cause. The written notice, which documents the reason for the suspension or early termination, must be delivered by the executing party of the suspension. The PI must inform the study participants, the CI and the CEI as soon as possible, providing the reasons.

The situations in which the suspension or early termination of the study will be considered include, but are not limited to:

1. Presence of serious adverse events in more than 10% of the participants in each intervention group.
2. The competent authority (COFEPRIS) considered it for security alerts.
3. The Sponsor determined it for your convenience or eventualities such as: economic support, manufacturing errors, etc.
4. Less recruitment than stipulated.
5. Determination of unexpected risks for participants, which are significant or unacceptable.
6. Obtaining new relevant safety information.
7. Insufficient adherence to protocol requirements.
8. The data obtained are not evaluable or are not sufficiently complete.
9. Determination that the primary objective has been reached.
10. Determination of futility.

In case of suspension, the study can be resumed once the situations that led to suspension have been remedied; as long as this justification is sufficient for the sponsor, CI, CEI and regulatory authorities.

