At the counting stage, the participant number will be assigned consecutively, using 3 consecutive digits. Once the subject has been selected, he will be assigned a number with which he will be identified throughout the study. Said code will be composed of eight numbers in the following order from left to right:

- three digits of the molecule under study according to the denomination by the sponsor.
- two digits corresponding to the research center number.

- three digits of the number consecutive to its inclusion assigned to the research center.

Example:

6.3 Intervention.

The subjects will be divided into two equal groups, to which they will be assigned randomly and blinded to one of the products in research (PI) PRO-179 or Travatan®.

Dosage: 1 drop every 24 hours, at night, in both eyes.

Instructions for administration: instillate a drop in the conjunctival sac, it is recommended to exert gentle traction on the lower eyelid, with the index finger, to expose the cul-de-sac and instillation. Avoid blinking energetically for the next few minutes or closing your eyes in a forced way.

Duration of the intervention: 10 days.

6.3.1 Medications administered.

6.3.1.1 Drug under study.

- Generic name: Travoprost
- Distinctive denomination: Bristrio® (PRO-179)
- Active principles: Travoprost 0.004%.
- Pharmaceutical form: Ophthalmic solution
- Presentation: multi-dose dropper bottle, 2.5 ml.
- Prepared by: Sophia Laboratories, S.A. of C.V.
- Description of the solution: transparent solution, free of visible particles.
- Description of container: White bottle with 5mL capacity, made of low density polyethylene.

Agent	Quantity mg / mL	Function
Travoprost	0.040	Active principle
Hydroxypropylbetacyclodextrins	Not showing	Stabilizer
Mannitol	Not showing	Toning
Boric acid	Not showing	Buffer Agent
Sodium Borate Dehydrated	Not showing	Buffer Agent
Disodium edetate Dihydrate	Not showing	Chelating Agent
Benzalkonium Chloride (1)	Not showing	Conservative
Water for the preparation of Injectables c.b.p.	1.000 mL	Vehicle

Table 2. Quali-quantitative formulation of PRO-179

6.3.1.1 Reference medicine.

- Generic name: Travoprost
- Distinctive denomination: Travatan®
- Active ingredients: Travoprost 0.004%
- Pharmaceutical form: Ophthalmic solution.
- Presentation: multi-dose dropper bottle, 2.5 ml.
- Prepared by: Alcon Laboratories Inc.
- Description of the solution: transparent solution, free of visible particles.
- Consult information to prescribe.

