6.3.2 Strategies to improve adherence and procedure to monitor adherence.

1. 1. Direct questioning by the PI about the application of the IP.
2. 2. Delivery of a printed calendar specifying the date of the visit and its activities.
3. 3. Journal of the subject.

6.3.2.1 Procedure to monitor adherence.

For more than four decades, there have been numerous investigations on the proper way to measure and quantify adherence to medications, however none has reached consensus to establish itself as the gold standard, both in cross-sectional and longitudinal studies. [48, 49, 50, 51, 52, 53, 54, 55]

There are different procedures to measure the adherence of pharmacological interventions. The most common procedure includes self-reports, these include: patient interviews, questionnaires and self-monitoring journals. Its strengths are speed, flexibility, low cost and ease of implementation; they have a high degree of specificity for non-adherence, nevertheless, the sensitivity and reliability for adherence is low. [55, 56]

The biochemical measurement of the drug, or its metabolite, is one of the methods that best confirms the use of the drug. Nevertheless, in addition to raising costs and being impractical, it is of little use in the context of ophthalmic applications, since concentrations at the peripheral level could be undetectable; and samples from other tissues imply more invasive methods that would not be advisable. [55]

Medication counting is another way to measure adherence. Classically referred to as "pill counting", in ophthalmology it is translated to the weight of the bottle. This is a simple, economical and non-invasive method. The main disadvantages of this method are: 1. The application of the medication can not be confirmed (it could have been intentionally thrown or instilled out of the eye) and 2. It depends on the subject bringing back the medication. [55, 56]

For the purposes of this study, the evaluation of the adherence will be favored by means of the diary of the subject, and will be carried out in the following way:

$$Ad = (A_r)100/A_i$$

Ad = Adherence

Ar = Registered applications

Ai = Applications indicated for the IP

The final adhesion will be determined by the average of the adherence of each one of the visits. Overall adherence (all subjects) will be determined by the average final adherence of each of the subjects.

6.3.3 6.3.3 Treatments and concomitant medications allowed and prohibited during the study.

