The designated personnel will perform the extraction of the blood sample, through venipuncture. The vein will be chosen at the discretion of the personnel in charge and will perform asepsis of the skin of the area to be punctured prior to the procedure. It will generate the order of the studies of BH, QS and PFH, to be carried out by the clinical laboratory designated by the sponsor. The clinical laboratory will deliver to the the results for its assessment and registration. The normal parameters to be considered will be the ranges established by the laboratory, with a lower and superior margin of 20% in a clinically healthy subject, at the discretion of the PI.

6.4.4 Measurement time.

The measurements of the variables of primary and secondary outcome, as well as the activities contemplated in the protocol, will be carried out and evaluated for each visit, according to the following:

Basal Visit / Day 1.

Some of these measurements will be taken at the screening visit to complete the eligibility criteria, at the discretion of the PI, they may be taken to complete the baseline visit data.

1. 1. Eye comfort index.
2. 2. Visual ability
3. 3. Vital signs
4. 4. Evaluation of ocular surface.
5. to. It includes stains.
6. 5. Intraocular pressure.
7. 6. Comprehensive ophthalmological evaluation.
8. 7. Evaluation of adverse events.
9. 8. Evaluation of results of laboratory tests.

Visit 1 / Day 5.

1. It can be done in a period \pm 1 days in relation to the 4th day of application.
2. 1. Visual ability
3. 2. Intraocular pressure.
4. 3. Evaluation of ocular surface.
5. to. It includes stains.
6. 4. Comprehensive ophthalmological evaluation.
7. 5. Vital signs
8. 6. Evaluation of adverse events.

Final Visit / Day 11.

1. It can be done in a period + 1 day in relation to day 11, not before day 11 since the 10 days of application would not be fulfilled.
2. 1. Visual ability
3. 2. Intraocular pressure.
4. 3. Eye comfort index.
5. 4. Evaluation of ocular surface.
6. to. It includes stains.
7. 5. Comprehensive ophthalmological evaluation.
8. 6. Vital signs
9. 7. Evaluation of adverse events.

Security call / Day 14.

1. It can be done in a period \pm 1 day in relation to the 14th day of the start of application.
2. 1. Ask about the presence of an adverse event.
3. 2. Evaluation of results of laboratory tests.

6.5 Timeline and study diagram.

Procedures	Scrutiny	VB	V1	VF	LIS
	D 1 - X ^a	D 1	D 5 ± 1	D 11 a + 1	D 14 ± 1
CI Signature	X				
Clinic history	X				

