- Urine pregnancy test: Refers to the performance of a rapid pregnancy test in all women of childbearing age who wish to enter the study. By fertile age we understand women who have presented their menarche and have not presented their menopause. Menopause is defined as 12 months from the last menstruation in women over 40 years of age; or those who underwent bilateral hysterectomy or oophorectomy. Women of childbearing age with contraceptive methods including bilateral tubal obstruction should be tested for pregnancy. This test will be done by the PI or the designated team person according to the instructions of the device delivered by the sponsor.
- Vital signs: see 6.4.3.7 Vital signs.
- Visual capacity: see 6.4.3.1 Visual capacity.
- Comprehensive ophthalmological evaluation: see 6.4.3.2 Comprehensive ophthalmological evaluation.
- Integrity of the ocular surface: see 6.4.3.4 Integrity of ocular surface:
- Intraocular pressure: see 6.4.3.6 Intraocular pressure.
- Eligibility criteria: refers to the review by the PI, where it states that the subject can be included in the study by meeting the inclusion criteria and not meeting the exclusion criteria. See 6.2.1 Selection criteria.
- Sampling of laboratory samples: see 6.4.3.8 Laboratory tests.
- Adverse events: see 6.4.3.5 Presence of adverse events.

6.5.1.2 Basal visit.

- Review of laboratory tests: refers to the review and analysis by the PI of the results of the BH, QS and PFH.
- Eligibility criteria: with the results of the laboratory the profile of the subject will end for its inclusion or not.
- Evaluation of variables: The data of the evaluation of the variables listed below can be taken from the scrutiny visit. It is the prerogative of the PI to decide whether to use the information from the screening visit or to repeat the evaluations in this visit.
 - Intraocular pressure
 - Visual capacity
 - Integrity of the ocular surface

- Comprehensive ophthalmologic evaluation
- vital signs
- Eye comfort index: see 6.4.3.3 Eye comfort index.
- Assignment of IP: Refers to determine the intervention that the patient will follow during the study. It will be done according to the Methods section. Assignment of the intervention. This assignment will be made at the baseline visit (day 1) and will go along with the indication to start the treatment period at night.

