- Intra-group analysis: will be determined by the Wilcoxon rank test, for quantitative variables [65]
- Inter-group analysis: will be determined by the Mann-Whitney U test Kruskal-Wallis. This non-parametric test will be used to test whether a group of data comes from the same

population. Intuitively, it is identical to the ANOVA with the data replaced by categories using the student's t statistic.

The level of difference to consider significance will be an alpha of 0.05 or less.

The result of nominal and ordinal qualitative variables will be presented in frequencies, proportions and percentages, see table 3 (section 6.4.3).

The statistical analysis to identify significant differences of the qualitative variables will be done creating 2x2 contingency tables and it will be done in the following way:

- Intra-group difference: McNemar test [66]. Which is applied to 2×2 contingency tables with a dichotomous trait, with pairs of matched subjects, to determine if the marginal frequencies of row and column are equal (marginal homogeneity).
- Inter-group difference: Pearson's χ^2 test (or Fisher's exact).

The level of difference to consider significance will be an alpha of 0.05 or less.

For the reporting of adverse events all eyes of those participants who were randomly assigned to an intervention group after the baseline visit will be considered. The results will be expressed in number of cases (eyes).

The final report of the results will be shown in tables or graphs, as appropriate.

It will be considered that the investigational drug is safe and tolerable when there are no clinical and statistical differences in all the variables of primary outcome, with respect to its comparators.

Those subjects who comply with an adherence greater than 60% will be included in the statistical analysis to meet the objective of the study, taken from the subject's diary. It was considered that from the minimum dose necessary to obtain a pharmacological effect (hypotensive / 1 application per day) and the presence of adverse events (exposure) is sufficient to meet the overall design objective, according to the pharmacological characteristics of the IP.

8.3.2 Additional analyzes.

No additional analyzes are contemplated to those previously described. Nevertheless, these may be performed if during the conduction of the study it is required to analyze specific safety aspects of any intervention, maintaining the blinding until the end of the study.

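### Final adherence is an unweighted mean of two visit percentages, so when Visit 1 falls on day 4 the over-60% rule can pass a subject with 5 of 10 doses and fail one with 7 of 10

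*Combined protocol and SAP*

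**What the plan says.** Section 6.3.2.1 defines adherence as 100 times registered applications over indicated applications, taken from the subject's diary ("Ar = Registered applications"). It then combines the visits: "The final adhesion will be determined by the average of the adherence of each one of the visits". No weighting is given there or elsewhere.

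The schedule in 6.5 places the adherence evaluation at two visits, Visit 1 and the final visit. Under 6.5.1.3 the diary is handed in at Visit 1 and a diary is delivered again.

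On dosing, section 6.3 gives "Dosage: 1 drop every 24 hours, at night, in both eyes" and "Duration of the intervention: 10 days". Section 6.5.1.2 says that assignment at the day 1 visit "will go along with the indication to start the treatment period at night". Section 6.4.4 allows Visit 1 one day either side, "in relation to the 4th day of application", and does not allow the final visit before day 11.

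Section 8.3.1 sets the cut: "Those subjects who comply with an adherence greater than 60% will be included in the statistical analysis to meet the objective of the study". The same section reports adverse events on all randomised participants, with no adherence condition. Section 8.3.3 describes an intention-to-treat analysis of participants who completed Visit 1, also with no adherence condition.

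**The concern.** Section 8.3.1 justifies the 60% cut by exposure: enough applications for a pharmacological effect and for adverse events to appear. Exposure over a fixed course is the number of doses taken. A plain average of two interval percentages equals the share of doses taken only when both intervals hold the same number of doses. Otherwise a dose in the shorter interval counts for more. Two subjects with the same dose total can then fall on opposite sides of the cut because of which doses they missed, and one dose record can pass or fail according to which permitted day Visit 1 took place.

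What is at stake is membership of the adherence-restricted analyses, including the ICO score, in a trial with 12 subjects per arm. One subject is 1/12, about 8% of an arm.

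**Working it through.** The plan states no numerical adherence result to reproduce. The check compares its rule with the share of all doses taken, over every possible dose pattern.

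**Inputs**
- One application per night for 10 nights, starting on the night of day 1 (6.3, 6.5.1.2): 10 indicated applications.
- Visit 1 on day 5 ± 1 (6.4.4, 6.5). Doses before Visit 1, n1: 3 on day 4, 4 on day 5, 5 on day 6. Doses after it, n2 = 10 − n1: 7, 6 or 5.
- Inclusion requires strictly more than 60% (8.3.1).
- Assumption: each visit percentage covers the interval since the previous visit. The diary exchange at Visit 1 supports this, but 6.3.2.1 does not say it.

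**Formulas**, with a doses taken before Visit 1 and b after it
- Plan: average = 100 × (a/n1 + b/n2) / 2.
- Dose total: pooled = 100 × (a + b) / 10.
- Difference: average − pooled = 100 × (a/n1 − b/n2) × (n2 − n1) / 20. The largest possible gap is therefore 100 × 4/20 = 20 percentage points at 3/7, 100 × 2/20 = 10 points at 4/6, and zero at 5/5.
- Weight of a dose before Visit 1 relative to one after it: n2/n1 = 7/3 = 2.3 at 3/7, 6/4 = 1.5 at 4/6, and 1 at 5/5.

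**Patterns where the two measures fall on different sides of the cut**

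| Visit 1 | Pattern | Pooled | Average | Under the plan |
|---|---|---|---|---|
| Day 4 (3/7) | 3/3 + 2/7 | 50% | (100 + 28.6)/2 = 64.3% | included |
| Day 4 | 2/3 + 4/7 | 60% | (66.7 + 57.1)/2 = 61.9% | included |
| Day 4 | 3/3 + 3/7 | 60% | (100 + 42.9)/2 = 71.4% | included |
| Day 4 | 0/3 + 7/7 | 70% | (0 + 100)/2 = 50.0% | excluded |
| Day 4 | 1/3 + 6/7 | 70% | (33.3 + 85.7)/2 = 59.5% | excluded |
| Day 5 (4/6) | 4/4 + 2/6 | 60% | (100 + 33.3)/2 = 66.7% | included |
| Day 5 | 3/4 + 3/6 | 60% | (75 + 50)/2 = 62.5% | included |
| Day 6 (5/5) | none | | | |

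There are five discordant patterns at 3/7, two at 4/6 and none at 5/5.

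**Edges at the nominal day.** At 4/6 the highest average with 5 of 10 doses is (100 + 16.7)/2 = 58.3%, excluded. The lowest with 7 of 10 is (25 + 100)/2 = 62.5%, included. So at day 5 a subject with half the doses is never admitted and one with 70% is never dropped.

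**Sensitivity to the reading**
- If the final-visit percentage were cumulative over all 10 doses, the nominal day would be affected too: 4/4 then 5/10 gives (100 + 50)/2 = 75%, and 1/4 then 7/10 gives (25 + 70)/2 = 47.5%.
- If applications were counted per eye (8 and 12 at the nominal day), 8/8 + 3/12 (11/20 = 55%) gives (100 + 25)/2 = 62.5%, included, and 1/8 + 12/12 (13/20 = 65%) gives (12.5 + 100)/2 = 56.3%, excluded. The results for 50% and 70% taken at 4/6 do not change.

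**The case against.** The strongest reply is that nothing here is miscalculated. The plan predefines its own measure and cut-off, 6.3.2.1 itself says that no adherence measure is a gold standard, and no section states that 60% means a share of all ten doses. That stands in part: this is a choice of definition, not an arithmetic error. But the plan's own reason for the cut is exposure, and total doses measure exposure where an unweighted visit average does not.

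Three stronger inferences are tempting, and the documents do not support them.

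- A reader might infer that the rule generally admits subjects with half the doses and drops those with 70%. It does so only when Visit 1 is on day 4. At nominal day 5 the discordance is confined to exactly 6 of 10 doses, where it turns on the cut being strict.
- A reader might infer that the rule decides who enters the analysis of both primary outcomes. Adverse-event reporting in 8.3.1 covers all randomised participants. Of the two primary outcomes only ICO is exposed, and if 8.3.3 governs, the adherence figure does not affect inclusion at all.
- A reader might infer a bias tied to tolerability, since someone who stops late from discomfort is scored more leniently than someone who misses doses early. The plan does not show this. Intolerance of the study drugs is an elimination criterion in 6.2.1.3, and 6.5.1.6 substitutes an early termination visit, so the 3/7 or 4/6 denominators may not apply to such subjects.

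It is also fair to say that the affected patterns need a healthy volunteer to miss three to five of ten doses despite reminders, a calendar and a diary. The documents give no basis for estimating how often that would happen.

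**Conclusion.** The point holds as a minor defect of definition. With Visit 1 on day 4, the over-60% rule can admit a subject with 50% of doses (score 64.3%) and exclude one with 70% (50.0% or 59.5%). At nominal day 5 the only effect is to admit some subjects at exactly 60%, and at day 6 there is none. Every affected subject has missed at least three of ten doses.

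The consequence is limited to ICO and the other analyses restricted by adherence, and it arises only if the 60% rule in 8.3.1 stands alongside the intention-to-treat statement in 8.3.3. Those two sections need to be reconciled in any case.

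The conclusion assumes ten indicated applications, each night counted once, interval-specific percentages, and that the 60% rule uses the final adherence of 6.3.2.1, the only per-subject summary the plan defines.

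**What to change.** In 6.3.2.1, define a subject's final adherence as 100 × total registered applications / total indicated applications over the whole treatment period, and use that figure wherever 8.3.1 applies the 60% cut. Then 5/10 is 50% and 7/10 is 70% whatever the day of Visit 1, and the question of interval or cumulative percentages no longer affects inclusion. In the same edit, state whether the 60% rule or the set in 8.3.3 governs each non-adverse-event analysis.

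The cost is one line of wording for the adherence definition and a sentence for the reconciliation. The diary data are already collected, and neither the threshold nor any clinical procedure changes.
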